### 3.1

### **Part 1 Dose Escalation**

Each of the fasting cohorts will be dosed in 2 groups. The first cohort will start with a sentinel group. The decisions on continuing of dosing Group 2 (at least 24 hours after dosing of Group 1) will not take place until the Sponsor, in conjunction with the Principal Investigator, has determined adequate safety and tolerability.

#### Dose Escalation Review

A review period will take place after the dosing of all subjects in each cohort in order to evaluate and interpret all pharmacokinetic and safety data collected.

The review of all pertinent safety/tolerability data will include physical and neurological examinations, ECGs, vital signs, clinical laboratory tests, cardiac monitoring, and AEs or serious adverse events (SAEs) through Day 4. Also, data from the current dose cohort and all previous cohorts will be considered.

The Sponsor and Investigator will determine if there are sufficient data available from all subjects to make a dose escalation decision. Any AEs of grade  $\geq 2$  toxicities (per Division of Microbiology and Infectious Disease [DMID] toxicity table; Appendix 3) must be considered in the decision to escalate to the next dose level. ECG data will be analyzed in a blinded fashion and unblinded by ECG vendor in order to be presented by treatment group in aggregate (reviewers will not be unblinded by subject).

Pharmacokinetic analysis will be completed only on the active treatment subjects and will be blinded to subject. Blinding will also extend to others who are intimately involved with the study except for the designated unblinded pharmacy staff and in cases of medical emergencies.

Upon review of relevant cohort data, the Sponsor, in conjunction with the Investigator may decide to:

- 1: Escalate the dose as planned
- 2: If concerns arise from pharmacokinetic and safety data that do not warrant ceasing escalation:
  - a: evaluate an intermediate dose level prior to the next planned dose level;

OR

- b: repeat a given dose level in a new cohort of subjects
- c: Repeat a dose level using a different dosage formulation.

3. Add a cohort or increase the dose of the next cohort if the bioavailability is lower than expected in the previous cohort and there were no safety concerns.
4. Halt the study.

The next dose in the escalating phase of the SAD study will be guided by emerging safety and PK data. After each cohort, Bayesian linear models will be fitted to the data from all available cohorts with log-transformed  $C_{max}$  as the response variable and log-transformed dose as the predictor variable. Different prior distributions on the coefficient of log-transformed dose, representing different assumptions about dose proportionality, will be considered. Predictive distributions will be generated for  $C_{max}$  at doses to be considered for the next level of escalation. These predictive distributions, together with emerging safety data, will be assessed by the clinical team to reach a decision on the next dose. Key features of the predictive distributions to be evaluated are the median  $C_{max}$  and the number of subjects out of those receiving TBI-223 in the next cohort expected to have  $C_{max}$  exceed 20.2  $\mu\text{g}/\text{mL}$ . (the NOAEL plasma  $C_{max}$  in the 28-day GLP dog toxicity study).

### **3.2 Stopping Rules for Cohorts**

If any of the cohort stopping rules are met, cohort dosing must be stopped until review of the data by the Sponsor and the Investigator.

Rules for stopping dosing of a cohort include the following:

1. Two or more subjects experience drug-related SAEs;
2. Two or more subjects experience grade 2 or higher (per DMID toxicity table; Appendix 3) central nervous system (CNS) AEs considered related to drug.
3. Two or more subjects develop drug-related QTcF prolongation greater than or equal to 500 msec or a change from baseline greater than 60 msec, after completing repeat testing.
4. Two or more subjects experience drug-related Grade 3 or Grade 4 cardiac rhythm cardiac disturbances.

## **4 IDENTITY OF INVESTIGATIONAL PRODUCT**

The Investigational Medicinal Product (IMP) will be supplied as TBI-223 25 mg/mL oral suspension or matching placebo.

Refer to Appendix 2 for details regarding the description and composition of TBI-223.

**Table 3 Identity of Investigational Product**

Part 1	
Test Product:	TBI-223 oral suspension 25 mg/mL
	Manufactured for Global Alliance for TB Drug Development
Control Product:	Placebo for TBI-223 oral suspension
	Manufactured for Global Alliance for TB Drug Development
Test Product: Cohort 3b	TBI-223 Oral Enteric Capsules, 150 mg
	Manufactured for Global Alliance for TB Drug Development
Part 2	
Test Products: Cohort 8 (Arms 1-4)	TBI-223 SR Tablets 600 mg (Prototype 1)
	Manufactured for Global Alliance for TB Drug Development by Piramal Enterprise Limited
	TBI-223 SR Tablets 600 mg (Prototype 2)
	Manufactured for Global Alliance for TB Drug Development by Piramal Enterprise Limited
	TBI-223 SR Tablets 900 mg (Prototype 3)
	Manufactured for Global Alliance for TB Drug Development by Piramal Enterprise Limited
	TBI-223 IR Tablets 1000 mg
	Manufactured for Global Alliance for TB Drug Development by Piramal Enterprise Limited
Test Products: Cohort 9	TBI-223 IR Tablets 1000 mg
	Manufactured for Global Alliance for TB Drug Development by Piramal Enterprise Limited

## 5 SUBJECT SELECTION

### 5.1 Inclusion Criteria

All volunteers must satisfy the following criteria to be considered for study participation:

1. Understands study procedures and voluntarily provides written informed consent prior to the start of any study-specific procedures.
2. Is a healthy adult male or a healthy adult female, 19 to 50 years of age (inclusive) at the time of screening.

3. Has a body mass index (BMI)  $\geq 18.5$  and  $\leq 32.0$  ( $\text{kg}/\text{m}^2$ ) and a body weight of no less than 50.0 kg.
4. Is medically healthy with no clinically significant screening results, as determined by the Principal Investigator (e.g., laboratory profiles are normal up to and including Grade 1 per DMID toxicity tables; Appendix 3), medical history, vital signs, ECG, or physical/neurological examination findings. Note: If exclusionary lab criteria are met, values may be confirmed by repeat evaluation.
5. Has not used tobacco- or nicotine-containing products (including smoking cessation products), for a minimum of 6 months before dosing.
6. If female of non-childbearing potential, she has undergone one of the following sterilization procedures at least 6 months before dosing:
  - Hysteroscopic sterilization;
  - Bilateral tubal ligation or bilateral salpingectomy;
  - Hysterectomy; or
  - Bilateral oophorectomy;
  - Or is postmenopausal with amenorrhea for at least 1 year before the first dose with serum follicle-stimulating hormone (FSH) levels consistent with postmenopausal status (i.e., greater than 40 mIU/mL) at screening.

Or, if female of childbearing potential, must agree to use an allowable form of birth control from screening until 14 days after study completion. The following are allowed birth control methods for this study:

- Vasectomized partner (at least 6 months before dosing);
- Non-surgical permanent sterilization (e.g., Essure® procedure) at least 3 months before dosing;
- Double barrier method (e.g., diaphragm with spermicide; condoms with spermicide);
- Intrauterine device (IUD);
- Abstinence (and must agree to use a double barrier method if they become sexually active during the study);
- Implanted or intrauterine hormonal contraceptives in use for at least 6 consecutive months before study dosing; and/or
- Oral, patch, or injected contraceptives, or vaginal hormonal device (i.e. NuvaRing®), in use for at least 3 consecutive months before study dosing.

7. If a non-vasectomized male (or male vasectomized less than 120 days prior to study start) he must agree to the following during study participation and for 90 days after the last administration of study drug:
  - Use a condom with spermicide while engaging in sexual activity or be sexually abstinent
  - Not donate sperm during this time.

*In the event the sexual partner is surgically sterile or postmenopausal, use of a condom with spermicide is not necessary. None of the birth control restrictions listed above are required for vasectomized males whose procedure was performed more than 120 days before study start.*

8. Is willing to answer inclusion and exclusion criteria questionnaire at check-in.
9. Is able to comply with the protocol and the assessments therein, including all restrictions.
10. Is willing and able to remain in the study unit for the entire duration of the assigned confinement period(s), return for outpatient visit(s), and receive a phone call for follow-up questioning about AEs.
11. If enrolled in the food-effect cohort, is willing and able to consume the entire high-calorie, high-fat breakfast meal in the timeframe required.

## 5.2 Exclusion Criteria

Volunteers will be excluded from study participation for any of the following:

1. History or presence of clinically significant cardiovascular, pulmonary, hepatic, renal, hematological, gastrointestinal, endocrine, immunologic, dermatologic, neurological (including epilepsy), oncologic, or psychiatric disease or any other condition that, in the opinion of the Investigator, would jeopardize the safety of the subject or the validity of the study results.
2. Evidence on physical exam and targeted neurologic exam of specific findings such as resting or intention tremor, dysmetria, nystagmus or ataxia, or abnormal deep tendon reflexes (either zero or hyper-reflexia).
3. History of any illness that, in the opinion of the Investigator, might confound the results of the study or pose an additional risk to the subject by their participation in the study.
4. Surgery within the past 90 days prior to dosing as determined by the Investigator to be clinically relevant, or any history of cholecystectomy.
5. History or presence of alcoholism or drug abuse within the past 2 years as determined by the Investigator to be clinically relevant.

6. History of sensitivity or contraindication to use of linezolid, sulfa drugs, or any study investigational products.
7. Participation in another clinical trial within 30 days prior to dosing.
8. Female subjects who are pregnant or lactating.
9. Positive result on a urine drug/alcohol/cotinine screen at Baseline or check-in.
10. Seated blood pressure is less than 90/40 mmHg or greater than 140/90 mmHg at screening. Out-of-range vital signs may be repeated once for confirmation.
11. Seated heart rate is lower than 40 bpm or higher than 99 bpm at screening. Out-of-range vital signs may be repeated once for confirmation.
12. Any clinically significant ECG abnormality at Screening (as deemed by decision of the Investigator and the Sponsor's Medical Monitor).

*NOTE: The following may be considered not clinically significant without consulting the Sponsor's Medical Monitor:*

- Mild first degree A-V block (P-R interval <0.23 sec)
- Right or left axis deviation
- Incomplete right bundle branch block
- Isolated left anterior fascicular block (left anterior hemiblock) in younger athletic subjects
- Early repolarization
- Tall T waves
- RSR in V1/V2 consistent with right ventricular conduction delay (with acceptable QRS)
- Sinus rhythm or sinus bradycardia with sinus arrhythmia
- Minimal or moderate voltage criteria for left ventricular hypertrophy (LVH).

13. QTcF interval >450 msec for males or >470 msec for females at screening, Day -1, or Day 1 (pre-dose), or history of prolonged QT syndrome. For the triplicate ECGs taken at screening and on Day -1, the average QTcF interval of the 3 ECG recordings will be used to determine qualification.
14. Family history of long-QT syndrome or sudden death without a preceding diagnosis of a condition that could be causative of sudden death (such as known coronary artery disease, congestive heart failure, or terminal cancer).
15. History of 1 or any combination of, the following:

- Seizures or seizure disorders, other than childhood febrile seizures
- Brain surgery
- History of head injury in the last 5 years
- Any serious disorder of the CNS or related neurological system, particularly one that may lower the seizure threshold.

16. Lactose intolerant.
17. History or presence of allergic or adverse response to Listerine breath strips or aspartame.

#### Specific Treatments

18. Use of any prescription medication within 14 days prior to dosing.
19. Use of any of the following medications within 30 days before the first dose of study drug or during the study drug treatment period: monoamine oxidase (MAO) inhibitors (phenelzine, tranylcypromine), tricyclic antidepressants (amitriptyline, nortriptyline, protriptyline, doxepin, amoxapine, etc.), antipsychotics such as chlorpromazine and buspirone, serotonin re-uptake inhibitors (fluoxetine, paroxetine, sertraline, etc.), bupropion, agents known to prolong the QTc interval (erythromycin, clarithromycin, astemizole, type Ia [quinidine, procainamide, disopyramide] and III [amiodarone, sotalol] anti-arrhythmics, carbamazepine, sulfonylureas, and meperidine).
20. Use of any over-the-counter (OTC) medication, including herbal products and vitamins, within 7 days prior to dosing, except acetaminophen. Up to 3 grams per day of acetaminophen is allowed at the discretion of the Investigator prior to dosing.
21. Use of any drugs or substances known to be significant inhibitors of cytochrome P450 (CYP) enzymes and/or significant inhibitors or substrates of P-glycoprotein (P-gp) and/or organic anion transporting polypeptides (OATP) within 14 days prior to the first dose of study drug.
22. Use of any drugs or substances known to be inducers of CYP enzymes and/or Pgp, including St. John's Wort, within 30 days prior to the first dose of study drug.
23. Use of any drugs or substance known to lower the seizure threshold.

### Laboratory Abnormalities

24. Serum magnesium, potassium, or calcium laboratory values outside of the normal range at screening. If exclusionary lab criteria are met, values may be confirmed by repeat evaluation.
25. Positive results at screening for human immunodeficiency virus (HIV), hepatitis B surface antigen (HBsAg), or hepatitis C antibodies (HCV).

### **5.3 Medication and Activity Restrictions**

1. Subject must not donate blood from 56 days or plasma from 7 days prior to the first dose of study medication until after the follow-up phone call. It is recommended that blood/plasma donations not be made for at least 30 days after discharge from the clinic.
2. Subject must not use tobacco- or nicotine-containing products (including smoking cessation products) from 6 months prior to the first dose of study medication until after the follow-up phone call.
3. Subjects must not consume alcohol from 72 hours prior to the first dose of study medication until after discharge from the clinic.
4. Subject must not consume beverages or foods that contain grapefruit or Mandarin oranges from 10 days before the first dose of study medication, or poppy seeds, broccoli, Brussels sprouts, pomegranate, star fruit, char-grilled meat, or caffeine/xanthine from 48 hours before the first dose of study medication, until after discharge from the clinic. Subjects will be instructed not to consume any of the above products; however, allowance for an isolated single incidental consumption may be evaluated and approved by the study Investigator based on the potential for interaction with the study drug.
5. Subject should avoid large quantities of foods or beverages with high tyramine content 48 hours prior to the first dose of study medication until discharge from the clinic. Quantities of tyramine consumed should be less than 100 mg per meal. Foods high in tyramine content include those that may have undergone protein changes by aging, fermentation, pickling, or smoking to improve flavor, such as aged cheeses (0 to 15 mg tyramine per ounce); fermented or air-dried meats (0.1 to 8 mg tyramine per ounce); sauerkraut (8 mg tyramine per 8 ounces); and soy sauce (5 mg tyramine per 1 teaspoon). The tyramine content of any protein-rich food may be increased if stored for long periods or improperly refrigerated.
6. Subject must not engage in strenuous exercise from 48 hours prior to the first dose of study medication until after discharge from the clinic.

7. Subject must be willing to remove any artificial nails (e.g., acrylic, gel) or fingernail polish and not use such products for the duration of the study.
8. Subject must not take any adrenergic/serotonergic agonists, such as pseudoephedrine and phenylpropanolamine (frequently found in cold and cough remedies), within 7 days before the first dose of study drug or during the study drug treatment period.

#### **5.4 Screening**

The informed consent documents (ICDs) will be discussed with each potential participant, and each individual will sign an ICD for the study prior to any study-specific procedures being performed.

Each potential study participant will have the following assessments by the Investigator or designee within 28 days prior to study start:

- Demographic data, including sex, age, race, ethnicity, body weight (kg), height (cm), BMI (kg/m^2), and smoking habits.
- Medical history
- Serology tests for HIV, hepatitis B and C
- Clinical laboratory tests (hematology, coagulation, chemistry, and urinalysis)
- Serum pregnancy (all female subjects)
- FSH test (female subjects claiming post-menopausal status)
- Urine test for drugs of abuse, alcohol, and cotinine
- Physical and neurological examinations
- Triplicate 12-lead safety ECGs
- Vital signs (blood pressure, pulse rate, respiration rate, temperature, and pulse oximetry)
- Concomitant medication review

Only medically healthy subjects with clinically acceptable laboratory profiles and ECGs within the defined parameters who fulfill all other inclusion criteria and meet none of the exclusion criteria outlined in the previous sections will be enrolled in the study.

Subjects will be assigned numbers in an ascending order, based on successful completion of the screening process.

### **6 STUDY PROCEDURES**

#### **6.1 Subject Assignment**

For Part 1, up to 50 subjects are planned to be enrolled in the study. Additional subjects may be enrolled if deemed appropriate by the Sponsor to repeat a dose level or to study another dose level. For Part 2, Cohort 8, 24 subjects will be enrolled. For Part 2,

Cohort 9, the 6 subjects from Cohort 8 who received the IR tablet formulation fasted will return after a 7-day washout and receive the IR tablet formulation under fed conditions. If more than 2 subjects of these 6 subjects from Cohort 8 drop-out, they will be replaced by healthy volunteers (a minimum of 4 subjects are needed to complete Cohort 9).

The number of subjects selected for the study was based on the adequate number considered to provide sufficient safety data. This study has not been formally powered.

For Part 1, each subject will receive an assigned treatment (active or placebo) based on the randomization schedule prepared by the unblinded statistician. The unblinded pharmacy staff will ensure compliance with the randomization schedule.

Note: the repeat cohort using a different dosage formulation in Part 1 and subjects in Part 2 will be non-randomized and unblinded; see Appendix 5 and Appendix 6.

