## Part 2:

Cohort 8: A minimum of 24 subjects in 4 dosing arms are planned to be enrolled; within each arm, 6 subjects will be assigned to receive a single dose treatment. Subjects will be assigned to one of the following arms and dose:

- Arm 1 – TBI-223 SR Tablets (Prototype 1) - 1800 mg dose (3 x 600 mg tablets), under fed conditions
- Arm 2 – TBI-223 SR Tablets (Prototype 2) - 1800 mg dose (3 x 600 mg tablets), under fed conditions
- Arm 3 – TBI-223 SR Tablets (Prototype 3) - 1800 mg dose (2 x 900 mg tablets), under fed conditions
- Arm 4 – TBI-223 IR Tablets - 2000 mg dose (2 x 1000 mg tablets), under fasting conditions

Procedures and analyses will be conducted as outlined in Appendix 6.

Cohort 9: The 6 subjects from Cohort 8, Arm 4, who received the IR tablet formulation fasted will return after a 7-day washout and receive a single dose of TBI-223 IR Tablets, 2000 mg dose (2 x 1000 mg tablets), under fed conditions.

If more than 2 subjects of these 6 subjects from Cohort 8 drop-out, they will be replaced by healthy volunteers (a minimum of 4 subjects are needed to complete Cohort 9).

Procedures and analyses will be conducted as outlined in Appendix 6.

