1 INTRODUCTION

This document details the planned statistical analyses for the Global Alliance for TB Drug Development, protocol “TBI-223-CL-001” study titled “A Phase 1, Partially-Blinded, Placebo-Controlled, Randomized Single Ascending Dose (SAD) with a Food Effect Cohort Study to Evaluate the Safety, Tolerability, and Pharmacokinetics of TBI-223 in Healthy Adult Participants”. The proposed analyses are based on the contents of protocol version 3.0, dated 21-Jan-2020 and Protocol Clarification Letter No. 4, dated 24-Feb-2020.

This is a partially blinded, placebo-controlled, randomized, SAD study with a food effect cohort. The study will be conducted at one study center in the United States.

Part 1

Part 1 of the study will have up to 6 planned dose levels. Based on interim pharmacokinetic data obtained during the dose escalation, a dose cohort will be selected to return for additional dosing after a high-calorie, high-fat meal (food-effect cohort).

Part 2

Part 2 of the study will comprise 4 arms each consisting of 6 subjects. Subjects will be assigned to one of the following dosing arms:

Arm 1	TBI-223 SR Tablets (Prototype 1) - 1800 mg dose (3 x 600 mg tablets) under fed conditions
Arm 2	TBI-223 SR Tablets (Prototype 2) - 1800 mg dose (3 x 600 mg tablets) under fed conditions
Arm 3	TBI-223 SR Tablets (Prototype 3) - 1800 mg dose (2 x 900 mg tablets) under fed conditions
Arm 4	TBI-223 IR Tablets - 2000 mg dose (2 x 1000 mg tablets) under fasting conditions

*IR = Immediate Release; SR = Sustained Release

The 6 subjects from Arm 4, who received the IR tablet formulation will be brought back following a 7-day washout period to receive TBI-223 IR Tablets 2000 mg (2 x 1000 mg tablets), under fed conditions. If more than 2 of the 6 subjects drop-out, they will be replaced by healthy volunteers (a minimum of 4 subjects is required to complete the Fed cohort).

Additional cohorts may be enrolled if deemed appropriate (e.g. if bioavailability is lower than expected) by the Sponsor to repeat a dose level, to study other dose levels, change proposed

QMD Ref: Worldwide-TMP-ST-006-4.0 Effective: 12Aug2019	Governing QMD: Worldwide-SOP-ST-001
Confidentiality Statement	

This document is the property of Worldwide Clinical Trials Inc. and may not be duplicated, copied, altered or removed from company without prior approval from Worldwide Quality Assurance or in compliance with Worldwide Standard Operating Procedures.

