3.2 Pharmacokinetic Endpoints

Serial blood samples will be collected pre-dose and post-dose through 72 hours to determine concentrations of TBI-223 and its metabolite (M2) in plasma.

QMD Ref: Worldwide-TMP-ST-006-4.0 Effective: 12Aug2019	Governing QMD: Worldwide-SOP-ST-001
Confidentiality Statement	
This document is the property of Worldwide Clinical Trials Inc. and may not be duplicated, copied, altered or removed from company without prior approval from Worldwide Quality Assurance or in compliance with Worldwide Standard Operating Procedures.	

Worldwide Clinical Trials Controlled Quality Management Document			
 WORLDWIDE CLINICAL TRIALS	Sponsor:	TB Alliance	
	Protocol Number:	TBI-223-CL-001	
STATISTICAL ANALYSIS PLAN – PHASE 1			

Noncompartmental pharmacokinetic parameters of AUC_{last} , AUC_{inf} , C_{max} , T_{max} , C_{last} , T_{last} , $AUC_{Extrap\%}$, λ_z , and $T_{1/2}$ will be calculated from plasma concentrations of TBI-223 (parent) and TBI-223 M2 (metabolite); CL/F and V_z/F will be calculated for TBI-223 only.

For Part 1, pharmacokinetic parameters will be summarized by cohort using descriptive statistics. Dose proportionality will be assessed using the power model approach (Cohorts 1-7, under fasted conditions). The 90% confidence intervals for geometric mean ratios, fed-to-fasted, of AUC_{last} , AUC_{inf} , and C_{max} will be determined as appropriate for Cohort 5.

For Part 2, pharmacokinetic parameters will be summarized by cohort and treatment/arm using descriptive statistics. The 90% confidence intervals for geometric mean ratios, test-to-reference, of AUC_{last} , AUC_{inf} , and C_{max} will be determined as appropriate for Cohorts 8 and 9.

Additional pharmacokinetic parameters may be calculated if deemed appropriate.

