5 RANDOMIZATION

Each subject in Part 1 will receive an assigned treatment (active or placebo) based on the randomization schedule prepared by the unblinded statistician. The first cohort will be separated into two groups. A sentinel group of 3 subjects (2 active and 1 placebo) will be dosed at least 24

QMD Ref: Worldwide-TMP-ST-006-4.0 Effective: 12Aug2019	Governing QMD: Worldwide-SOP-ST-001
Confidentiality Statement	

This document is the property of Worldwide Clinical Trials Inc. and may not be duplicated, copied, altered or removed from company without prior approval from Worldwide Quality Assurance or in compliance with Worldwide Standard Operating Procedures.

Worldwide Clinical Trials Controlled Quality Management Document			
 WORLDWIDE CLINICAL TRIALS	Sponsor:	TB Alliance	
	Protocol Number:	TBI-223-CL-001	
STATISTICAL ANALYSIS PLAN – PHASE 1			

hours before the remaining 5 subjects (4 active and 1 placebo). The remaining cohorts will be dosed in 2 groups of 4 subjects each (3 active and 1 placebo), 24 hours apart. Based on exposure levels, subjects in one of the dose levels will return after a 7-day minimum washout or 5 half-lives of the drug (whichever is longer) to receive the same dose under fed conditions. All subjects and clinical staff (except for the unblinded pharmacy staff) will be blinded to treatment.

Subjects in Part 1 who participate in the repeat cohort will receive a different treatment formulation. In Part 2, subjects will be non-randomized and unblinded.

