Statistical comparison of the PK parameters of exposure (C_{max} , AUC_{last} , and AUC_{inf}) will be performed using an Analysis of Variance (ANOVA) model for a 2-way crossover design on the ln-transformed data with treatment as the fixed effects and subject as a random effect. Conclusions regarding the results of the statistical analysis of PK parameters across treatments will be based on the ratio of the geometric means expressed as a percent (100×Fed/Fasted) and the 90% confidence interval about the ratio. A lack of food effect will be demonstrated if the 90% confidence intervals are fully contained within the limits of 80.00% to 125.00%.

QMD Ref: Worldwide-TMP-ST-006-4.0 Effective: 12Aug2019	Governing QMD: Worldwide-SOP-ST-001
Confidentiality Statement	
This document is the property of Worldwide Clinical Trials Inc. and may not be duplicated, copied, altered or removed from company without prior approval from Worldwide Quality Assurance or in compliance with Worldwide Standard Operating Procedures.	

Worldwide Clinical Trials Controlled Quality Management Document			
 WORLDWIDE CLINICAL TRIALS	Sponsor:	TB Alliance	
	Protocol Number:	TBI-223-CL-001	
STATISTICAL ANALYSIS PLAN – PHASE 1			

Part 1; Cohort 3 Repeat:

Statistical comparison of the PK parameters of exposure (C_{max} , AUC_{last} , and AUC_{inf}) will be performed using an Analysis of Variance (ANOVA) model for a two-way crossover design on the ln-transformed data with treatment as a fixed effect and subject as a random effect. Conclusions regarding the results of the statistical analysis of PK parameters across treatments will be based on the ratio of the geometric means expressed as a percent (100 \times Test/Reference; TBI-223 oral enteric capsules, Cohort 3 repeat vs. TBI-223 oral suspension, Cohort 3) and the 90% confidence interval about the ratio. Similar bioavailability will be demonstrated if the 90% confidence intervals are fully contained within the limits of 80.00% to 125.00%.

Part 2; Cohorts 8 and 9:

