Statistical comparison of the PK parameters of exposure (C_{max} , AUC_{last} , and AUC_{inf}) will be performed using an Analysis of Variance (ANOVA) model for a parallel design on the ln-transformed data with treatment as a fixed effect. Conclusions regarding the results of the statistical analysis of PK parameters across treatments will be based on the ratio of the geometric means expressed as a percent (100 \times Test/Reference) and the 90% confidence interval about the ratio. The following comparisons will be made:

- IR, 2000 mg (2 x 1000 mg tablets) / FED (Cohort 9) vs. IR, 2000 mg (2 x 1000 mg tablets) / FASTED (Cohort 8)
- SR (Prototype 1, 2 or 3), 1800 mg (2 x 900 mg tablets) / FED (Cohort 8) vs. , 2000 mg (2 x 1000 mg tablets) / FASTED (Cohort 8)
- SR (Prototype 1, 2 or 3), 1800 mg (2 x 900 mg tablets) / FED (Cohort 8) vs. IR, 2000 mg (2 x 1000 mg tablets) / FED

Note: 1800 mg TBI-223 SR Tablets will be dose-normalized to 2000 mg for the purpose of statistical comparisons.

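### Cohort 8 places 24 subjects into four different treatments without randomisation or a stated rule, yet SR/IR conclusions rest on a treatment-only ANOVA

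*Protocol*

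**What the plan says.** Protocol 6.1 (Subject Assignment) says that "subjects in Part 2 will be non-randomized and unblinded; see Appendix 5 and Appendix 6". SAP section 5 agrees: "In Part 2, subjects will be non-randomized and unblinded". The randomisation schedule described in both documents covers Part 1 only, for active versus placebo.

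Cohort 8 has four arms of six. Arms 1–3 receive SR Prototypes 1, 2 and 3 at 1800 mg fed, and Arm 4 receives the IR tablet at 2000 mg fasted. On who goes into which arm, Protocol section 3 (Part 2) says only: "Subjects will be assigned to one of the following arms and dose".

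For the analysis, SAP 6.11 uses an "Analysis of Variance (ANOVA) model for a parallel design on the ln-transformed data with treatment as a fixed effect". It bases conclusions on the test/reference geometric mean ratio and its 90% confidence interval. Each SR prototype is compared with IR fasted (Cohort 8) and with IR fed (Cohort 9).

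**The concern.** Without randomisation, the arms may differ systematically in ways that affect exposure, such as sex, body weight, order of recruitment or dosing date. A model with treatment as its only term attributes any such difference to the formulation, and its confidence interval does not allow for it. SAP 6.6 describes baseline comparability and SAP 6.3 summarises PK by gender. Those displays could reveal a sex imbalance, but they do not adjust the ratios.

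The problem reaches both SR/IR comparisons, because the Cohort 9 IR fed group is planned to be the Arm 4 subjects brought back. At stake is how far a reader can trust an SR/IR ratio as a statement about the formulations.

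**Working it through.** **1. Is there a rule or reason anywhere in the supplied text?**

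| Place | What it gives |
|---|---|
| Protocol 3, Part 2 | Subjects are assigned; no method |
| Protocol 5.4 | Numbering only: "Subjects will be assigned numbers in an ascending order, based on successful completion of the screening process"; numbers are not linked to arms |
| Protocol 6.1 | Non-randomised; refers to Appendix 6 |
| Protocol Appendix 6 | No allocation method. Its one rationale concerns blinding and says everyone gets one treatment, which its own four-arm list contradicts |
| SAP 5 | Non-randomised; no method |
| SAP 1 | Analyses rest on "protocol version 3.0, dated 21-Jan-2020 and Protocol Clarification Letter No. 4, dated 24-Feb-2020"; the letter was not supplied |

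**2. Inputs.** From the documents: 4 arms × 6 = 24, which reproduces the planned enrolment, so residual df = 24 − 4 = 20. The documents give no CV, sex effect or sex split. Assumed: CV 20% and 30%; male/female exposure ratio r = 1.10, 1.25, 1.40; sex splits of 4:2 vs 2:4, and 5:1 vs 1:5 as an extreme. Nothing in the documents points to the extreme split.

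**3. Precision for scale (CV 30%, true ratio 100%).** s = √ln(1 + 0.30²) = 0.2936. SE = s√(2/6) = 0.1695. With t(0.95, 20) = 1.725, exp(±0.2924) gives a 90% CI of 74.7–134.0%. At CV 20% it is 82.1–121.8%.

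**4. Shift and coverage.** Shift = r^d, where d is the difference in the proportion of men (2/6 or 4/6); for example, 1.25^(4/6) = 1.160. Coverage of the 90% CI was obtained in two ways:
- (a) Simulation, 200,000 runs per case: four arms of 6, the other two arms split 3:3, and CV taken within sex. Mixing sexes within an arm inflates the residual.
- (b) Noncentral t with a pure shift and no such inflation.

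| Split | r | Shift | (a) CV 30% | (a) CV 20% | (b) CV 30% | (b) CV 20% |
|---|---|---|---|---|---|---|
| 4:2 vs 2:4 | 1.10 | 3.2% | 0.898 | 0.898 | 0.894 | 0.888 |
| 4:2 vs 2:4 | 1.25 | 7.7% | 0.896 | 0.894 | 0.870 | 0.834 |
| 4:2 vs 2:4 | 1.40 | 11.9% | 0.893 | 0.894 | 0.831 | 0.752 |
| 5:1 vs 1:5 | 1.10 | 6.6% | 0.881 | 0.861 | 0.878 | 0.851 |
| 5:1 vs 1:5 | 1.25 | 16.0% | 0.811 | 0.728 | 0.781 | 0.649 |
| 5:1 vs 1:5 | 1.40 | 25.1% | 0.724 | 0.592 | 0.641 | 0.401 |

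Convention (a) matches a sex imbalance. Under it the moderate split costs almost no coverage, partly because the unmodelled sex variation widens the interval.

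**5. Under simple randomisation (assuming 12 men and 12 women; 60,000 runs per case).** Over all allocations, coverage is 0.898–0.902 in the six combinations of r and CV, and mean log bias is at most 0.0007. Chance imbalance remains: a given SR/IR pair differs by at least 2 of 6 in sex about 40% of the time, and by at least 4 of 6 about 4% of the time.

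**6. Adding sex to the ANOVA (19 df, t = 1.729).** The contrast variance rises by a factor of 1.059 (moderate split) or 1.286 (extreme split). At CV 30%:
- Moderate: 0.1695 × √1.059 × 1.729 ≈ 0.302, giving 74.0–135.2%.
- Extreme: 0.1695 × √1.286 × 1.729 ≈ 0.332, giving 71.7–139.4%.

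Simulated coverage returns to 0.899–0.901 in all 12 cases.

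**The case against.** Non-randomisation is openly declared and consistent between protocol and SAP, so this is a choice and not a contradiction. A rule might sit in the clarification letter that was not supplied. The stakes are low: safety is the primary objective, the study is not powered, and the Part 2 intervals "will be determined as appropriate for Cohorts 8 and 9". The criterion "Similar bioavailability will be demonstrated if the 90% confidence intervals are fully contained within the limits of 80.00% to 125.00" belongs to the Cohort 3 repeat. A matching one covers the Cohort 5 food effect, and none is set for Part 2. A single site and narrow eligibility limit how different the arms can be. At a moderate imbalance the shift is small against an interval of 74.7–134.0%. Randomising would still leave chance imbalance, SR fed versus IR fasted would stay mixed with food, and SR fed versus IR fed would stay exposed to period, drop-out and replacement in Cohort 9.

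Most of this stands, and it is why the point is something to consider and not a major flaw. It does not supply a reason for leaving allocation open. The sample size is no defence, because randomising needs no extra subjects. Residual food and period confounding does not justify adding an avoidable allocation bias. Chance imbalance differs in kind from systematic imbalance: the ratio is unbiased on average over random allocations and the interval keeps its nominal coverage, which an unstated rule cannot guarantee.

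**Conclusion.** The concern holds, at modest weight. Four different treatments are filled by an unstated, non-random rule, and the planned SR/IR conclusions come from a model that cannot separate allocation from formulation. The absence of a rule is established only for the documents supplied.

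The size is illustrative and depends wholly on assumed CVs, sex effects and splits. Ratio shifts run from 3.2% to 11.9% at 4:2 vs 2:4, with simulated coverage of 89–90%. At the extreme 5:1 vs 1:5 they run from 6.6% to 25.1%, with simulated coverage of 88% down to 59%. The case rests on the missing rule and the unadjusted model, not on a predicted bias.

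**What to change.** **If allocation has not happened:** randomise the 24 Cohort 8 subjects open-label to four arms of exactly 6, using a schedule from the statistician who prepares the Part 1 list. Balance sex as far as arm size allows. If the sex counts are known beforehand, arms of 6 can be kept within one man of each other (14 men and 10 women give 4, 4, 3 and 3 men). With sequential enrolment, balance is approximate. Amend Protocol 6.1 and SAP 5, and check the Randomized Set in SAP 6.1.2, which these subjects would then enter.

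**If it has happened:** state the rule used (citing the clarification letter if it is there), label the SR/IR ratios descriptive, and add a sensitivity ANOVA with sex as a fixed effect.

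In either case, interpret SR fed versus IR fasted only as a combined formulation-plus-food ratio. As consequential wording, correct the single-treatment rationale in Appendix 6, and extend the exemption note in Protocol 6.2, which now covers only the Appendix 5 repeat cohort, to Part 2.

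**Cost:** a randomisation list and text changes, with no extra subjects. Separate sex-stratified lists could produce arms of 5 and 7, against Appendix 6's minimum of 6, so arm size should take priority. Every subject must be available for Cohort 9, since anyone may be drawn into Arm 4, and fed and fasted subjects may have to be dosed in the same sessions. Randomising Cohort 8 does not protect SR fed versus IR fed from Cohort 9 drop-out, replacement or period effects, and a sex term does not adjust for unmeasured factors.
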